2.5.6 Sample Size

This is a pilot study. We plan to study 30 evaluable subjects, assembled by *CYP2B6* genotyping, described previously (HRPO#201203033), to compose groups of 10 wild-type (*CYP2B6*1/*1*), 10 *CYP2B6* heterozygotes (*CYP2B6*1/*6*) and 10 *CYP2B6*6* homozygotes (*CYP2B6*6/*6*).

3.0 Management of Intercurrent Events

3.1 Adverse Experiences

The investigator will closely monitor subjects for evidence of adverse events. All adverse events will be reported and followed until satisfactory resolution. The description of the adverse experience will include the time of onset, duration, intensity, etiology, relationship to the study drug (none, unlikely, possible, probable, highly probable), and any treatment required.

3.2 Premature Discontinuation

If a subject withdraws from the study, the subject will be replaced in order to provide the required number of subjects. Subjects will be withdrawn if the investigator decides that discontinuation is in the best interest of the subject, or the subject requests withdrawal from the study.

3.3 Potential Risks

3.3.1 Potential risks from ketamine

Oral ketamine has been reported to produce fewer and milder adverse effects than parenteral ketamine, because lower peak plasma levels are reached after oral intake, there is extensive first-pass metabolism, the main metabolite norketamine reaches higher plasma levels, and norketamine might have a more favorable safety profile than ketamine.¹ The most frequently observed adverse effects of oral ketamine reported (across a range of doses) were effects on the central nervous system, such as sedation, somnolence, dizziness, sensory illusions, hallucinations, nightmares, dissociative feeling and blurred vision. Qualitatively similar adverse effects in patients were seen with intramuscular (0.4 mg/kg) and oral (4 mg/kg) ketamine, but there were fewer side-effects in the latter group, suggesting that adverse effects of oral ketamine are about one tenth that of intravenous ketamine. No distinction was made between effects of a single dose and effects after long term dosing.¹ Adverse effects of ketamine (0.1 mg/kg IV) in healthy volunteers were minimal.¹⁹ Based on prior experience with ketamine, the dose proposed (0.4 mg/kg oral, equivalent to 0.1-0.15 mg/kg IV), and prior published experience, some subjects may experience very mild drowsiness for about 1-2 hr after ketamine administration. As a precaution, volunteers are kept under observation if pharmacologic effects are present, and they are admonished to neither drive nor operate dangerous machinery for the remainder of the study day. Overall the risks associated with the use of ketamine in healthy volunteers are very small.

3.3.2 Other Potential Risks

Intravenous catheter placement can cause a bruise. The amount of blood drawn will not constitute a risk to subjects, since sessions are carefully timed to prevent phlebotomy from exceeding recommended limits. No psychological risks to subjects are envisioned.

3.4 Procedures to Minimize Potential Risks

The ketamine dose to be studied is subanesthetic, less than the recommended starting dose (0.5 mg/kg) for oral therapy in ketamine-naïve patients, and commensurate with that currently used in clinical studies (clinicaltrials.gov). Studies are conducted in the Washington University Department of Anesthesiology Research Unit under the general supervision of the PI, a board-certified anesthesiologist thoroughly trained and experienced in the administration of drugs, assessment of adverse effects, and their treatment. Subjects are monitored by trained (RN) nursing personnel. A urine pregnancy test will be performed on women of childbearing potential and subjects excluded if pregnant. Subjects will be informed that participation is voluntary and they may refuse to participate and may withdraw from the study at any time without penalty. Subjects will be told that in the event of a physical injury as the direct result of study procedures, they will be cared for by a member of the investigating team at no cost, within the limits of the Washington University compensation plan.

3.5 Data and Safety Monitoring Plan

The monitoring plan has been specifically developed to maximize research participant safety and for the protocols planned herein. In general, the PI has developed a specific set of Standard Operating Procedures (SOPs) for clinical research. All individuals working under the PI are required to read, be familiar with, and compliant with the SOPs. The specific monitoring plan for this investigation is commensurate with the risks and the size and complexity of the investigations planned. These risks, as described above, are small. The basic clinical protocol design has been used previously by the PI in hundreds of subjects, and the response to the drugs, adverse events (essentially only nausea and vomiting with opioids) and potential risks are well-characterized and well-known to the PI. Based on these considerations, we utilize a monitoring plan that involves:

- (1) engaging a colleague not involved in the study to serve in a monitoring capacity. Based on the small size and low-risk, we envision only a third person (the colleague), not a full DSMB.
- (2) a specific plan for submitting Adverse Event Reports to the IRB. That plan is detailed in the PI's SOP for Adverse Event Reporting (attached).

4. HUMAN SUBJECTS RESEARCH

4.1 Protection of Human Subjects

This study will involve normal subjects, whose participation will be strictly voluntary. This study is not a clinical trial which is designed to assess the safety and/or efficacy of drugs, devices, diagnostics, treatments, or preventive measures in humans for the treatment of any disease. The study will be covered under appropriate Washington University Institutional Review Board protocols and consent forms. The study will be conducted under the supervision of the PI, a Board-Certified and GCP-certified anesthesiologist with several years experience in the conduct of human volunteer studies.

4.2 Sources of Materials

For studies involving healthy volunteers, no medical records are used. Data on health and medication use are provided by subjects who fill out a health status questionnaire. Specimens include blood obtained exclusively for research purposes.

4.3 Recruitment and Informed Consent

Subjects will be approached for participation from a cohort of individuals previously genotyped for *CYP2B6* (HRPO approved protocol #201203033), in which subjects provide written consent for contact

and recruitment for additional research studies. Subjects with specific genotypes (*CYP2B6*1/*1*, *CYP2B6*1/*6* or *CYP2B6*6/*6*) will be invited to participate in this protocol. Subjects will be provided verbal and written descriptions of the study aims, procedures, risks, and benefits, and will be required to give written informed consent. A member of the investigative team provides all study descriptions, informed consent, and answers all questions. No deception is required for the purposes of this study. Subjects are informed verbally and in writing that participation is voluntary and they may refuse to participate and may withdraw from the study at any time without penalty.

4.4 Potential Benefits of the Proposed Research to the Subjects and Others

There is no benefit to individual subjects in this study. Society may benefit from a better understanding of ketamine metabolism, drug interactions and pharmacokinetics, leading to improved practice standards among clinicians.

4.5 Inclusion of Women

Studies and their advertisements actively encourage the participation of women in the research. As a matter of operational policy, our studies of healthy volunteers routinely and deliberately include equivalent numbers of women and men. To ensure sufficient enrollment of women, we typically close enrollment to men once their quota has been filled. This approach has been highly successful. Women of childbearing potential are not excluded from our research protocols. Pregnancy testing is performed as a matter of course to protect female research subjects, and subjects are instructed when appropriate to use adequate contraceptive measures.

4.6 Inclusion of Minorities

All of our studies and their advertisements actively encourage the participation of minorities in research. Our minority recruiting typically matches the demographic composition of the Washington University community from which subjects will be recruited (78% white, 21% Black, <1 % Hispanic). However, based on the higher incidence of *CYP2B6*6* allele in African-Americans, we anticipate a higher enrollment of minorities related to increased incidence of genotype.

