2. STUDY PROTOCOL

2.1 Background and Significance

Ketamine is a noncompetitive NMDA receptor antagonist, originally developed in 1964 as a "dissociative" anesthetic, and FDA approved in 1970. It can be administered by intravenous, intramuscular, oral, sublingual, intranasal, and rectal routes. Ketamine has been widely used for decades in anesthesia, in part, because unlike most other intravenous anesthetics, it does not significantly depress the respiratory and circulatory systems. In addition, ketamine causes significant anti-nociceptive and anti-hyperalgesic (i.e. analgesic) effects at low doses – lower than those which cause loss sedation and loss of consciousness.

More recently, there has been marked interest in the use of ketamine for other applications. Oral ketamine has been evaluated extensively for use in chronic pain management.¹ Use in pediatric sedation, analgesia, and emergency room analgesia is also of interest.²⁻⁵ More recently, has been the discovery that ketamine may be effective in the therapy of treatment-resistant depression, and with very fast response rates.⁶⁻⁹ A review of clinicaltrials.gov reveals a plethora of recent studies on ketamine. Thus there is very active research and clinical interest in ketamine.

Ketamine is administered clinically as a racemic mixture (R- and S-ketamine). Ketamine undergoes extensive metabolism, primarily via N-demethylation to norketamine, and to several other metabolites.¹⁰⁻¹³ First-pass metabolism of oral ketamine is considerable, thus it is only about 30% bioavailable. There are stereoselective differences in ketamine enantiomers metabolism and disposition. It has recently been established that cytochrome P4502B6 (CYP2B6) is the major isoform catalyzing ketamine N-demethylation *in vitro*, at therapeutic concentrations.¹⁴⁻¹⁶ A recent clinical investigation confirmed the predominant role of CYP2B6, and lack of significant CYP3A involvement, in ketamine pharmacokinetics and metabolism.¹⁷

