CYP2B6 is a highly polymorphic enzyme.¹⁸ The most common variant allele, *CYP2B6*6*, found most commonly in Africans, Africans-Americans, and some Asian populations, is associated with diminished hepatic CYP2B6 enzyme expression. Compared with wild-type *CYP2B6*1/*1*. A recent *in vitro* investigation demonstrated that CYP2B6.6 (the protein encoded by the *CYP2B6*6* allele) has diminished catalytic activity towards ketamine N-demethylation (compared with wild-type CYP2B.1, and liver microsomes from humans heterozygous or homozygous for the *CYP2B6*6* allele also had diminished catalytic activity towards ketamine N-demethylation, compared with *CYP2B6*1/*1*.¹⁶

Nonetheless, there is no formal evaluation of ketamine pharmacokinetics, metabolism or clearance in *CYP2B6*6* carriers. This investigation will formally address the role of *CYP2B6* polymorphism in ketamine disposition. The research proposed will test the hypothesis that *CYP2B6* variants (*CYP2B6*6* hetero or homozygotes) *in vivo* will have decreased ketamine metabolism and clearance.

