2.3 Patient Selection

Subjects will be recruited from the greater St. Louis community that has been identified as carriers of *CYP2B6* polymorphisms (identified by participation in Washington University HRPO approved study HRPO#201203033). Thirty evaluable, healthy male and non-pregnant female 18-50 yr volunteers, in approximately equal sex distribution, will be studied. Minorities will be actively sought and included, with minority composition to reflect that of the greater Washington University/St. Louis community.

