2.5.5 Statistical Methods

Plasma and urine ketamine and metabolite concentrations are analyzed by noncompartmental methods. Outcome measures in wild-type and *CYP2B6*6* carriers will be evaluated by ANOVA. If the hypothesis is correct, we will observe diminished ketamine metabolism and clearance in *CYP2B6*6* carriers.

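### Does the wild-type versus carrier ANOVA need a race-adjusted sensitivity analysis because the \*6 allele is commoner in African-Americans?

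*Protocol*

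**What the plan says.** - **Link between ancestry and genotype.** Protocol 2.1 describes the \*6 allele as "found most commonly in Africans, Africans-Americans, and some Asian populations". Section 4.6 gives the make-up of the "community from which subjects will be recruited (78% white, 21% Black, <1 % Hispanic"), then forecasts that enrolment will depart from it: "based on the higher incidence of *CYP2B6*6* allele in African-Americans, we anticipate a higher enrollment of minorities related to increased incidence of genotype".
- **Recruitment.** Section 2.3 aims for a sample "with minority composition to reflect that of the greater Washington University/St. Louis community". Section 4.3 states: "Subjects will be approached for participation from a cohort of individuals previously genotyped for" CYP2B6. Section 2.5.6 calls the study a pilot and plans "to compose groups of 10 wild-type", 10 heterozygous and 10 homozygous subjects. Nothing matches or stratifies the genotype groups by race.
- **Analysis.** Section 2.5.5 says: "Outcome measures in wild-type and *CYP2B6*6* carriers will be evaluated by ANOVA". The SAP repeats this. Neither document lists a covariate or a sensitivity analysis. Section 2.4.2, on bias, covers only coding and blinding to genotype.
- **Mechanism.** Section 2.1 says a clinical study "confirmed the predominant role of CYP2B6, and lack of significant CYP3A involvement" in ketamine disposition.
- **Size.** The SAP takes a 30% difference and an SD of 25%, and arrives at 12 per group.

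**The concern.** Genotype is not randomised here. If \*6 is commoner in African-Americans, selecting on \*6 will tend to put more Black subjects among the carriers than among the wild-type subjects. The planned ANOVA would attribute the whole group difference to genotype. If ancestry also changed the AUC ratio by some other route, the unadjusted contrast would carry that effect as well. It could inflate the \*6 effect and raise the false-positive rate, or work against it and hide the effect the study is meant to find. In a study of 30, an adjustment chosen after seeing the data would persuade few readers, so the absence of a pre-specified check looks like a gap.

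**Working it through.** Points below are percent of the wild-type mean.

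**1. The plan's own figure.** Inputs from the SAP: difference 30, SD 25. Alpha, sidedness and power are not stated; two-sided 5% and 80% are assumed. The normal approximation gives 2 × (1.96 + 0.84)² × (25/30)² = 10.9, so 11 per group. The t distribution gives 12 per group (power 80.2%), the SAP's number. For the Protocol's 10 wild-type against 20 carriers, the standard error is 25 × √(1/10 + 1/20) = 9.68 and power is 84.9%.

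**2. The two conditions for confounding.**

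| Condition | What the documents give |
|---|---|
| Ancestry is linked to genotype group | Stated in direction (2.1, 4.6), without frequencies by group |
| Ancestry affects the AUC ratio apart from \*6 | Nothing; 2.1 gives CYP2B6 the main role and reports no significant CYP3A part |

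Subjects are also selected by CYP2B6 genotype, so \*6 status is fixed by design. Other named CYP2B6 variants enter only through the investigator-discretion note in 2.3.1.

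**3. Size of a possible bias.** For the 10 v 20 contrast:

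bias = (ancestry effect apart from \*6) × (Black share in carriers − Black share in wild-type).

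If the first factor is 0, the bias is 0 whatever the imbalance. To obtain anything else, both factors must be assumed. The only documented share is 21% Black for the community as a whole. Assume an ancestry effect of 10 to 20 points, contained within the SD of 25:

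| Assumed Black share, wild-type / heterozygous / homozygous | Overall | Carriers − wild-type | Bias (points) | False positives | Power if a true 30-point effect is masked |
|---|---|---|---|---|---|
| 10/20/30% | 20% | 25 − 10 = 15% | 1.5 to 3 | 5.1 to 5.8% | 77 to 81% |
| 10/30/50% | 30% | 40 − 10 = 30% | 3 to 6 | 5.9 to 8.8% | 67 to 77% |

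The first row, whose overall share is close to the community figure, is practically nominal for false positives.

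**4. What the adjusted analysis could show.** Adding a Black v other term multiplies the variance of the genotype contrast by 1/(1 − R²), where R² = (1/3)(2/3) × (share difference)² / [p(1 − p)] and p is the overall share.

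- 10/20/30%: R² = 0.222 × 0.0225/0.16 = 0.031; inflation 1.032; power 84% if race has no effect.
- 10/30/50%: R² = 0.222 × 0.09/0.21 = 0.095; inflation 1.105; power 81%.

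The loss of power is small. The information gained is small too. The standard error of the race term is 25/√[30 × p(1 − p) × (1 − R²)]:

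- 10/20/30%: 25/√(30 × 0.16 × 0.969) = 11.6 points.
- 10/30/50%: 25/√(30 × 0.21 × 0.905) = 10.5 points.

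Power to detect a race effect is therefore about 13 to 15% for 10 points and 38 to 45% for 20 points. At a 10% share, the chance that no wild-type subject is Black is 0.9¹⁰ = 35%; the race effect would then be estimated from carriers alone.

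**5. Sections 2.3 and 4.6.** Section 2.3 states a recruiting aim. Section 4.6 starts from the same community composition and then explains why enrolment is expected to depart from it. An aim and a forecast can differ without contradiction; at most the wording could be tidied.

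**The case for a change.** The best case for the concern is that the omission is real and cheap to repair. The Protocol itself forecasts the imbalance. It calls the CYP2B6 role predominant, not exclusive, and mentions several other metabolites, so a second route is not excluded. Adjustment would not remove the \*6 effect, since genotype stays in the model. The SAP sizes a hypothesis test, so pilot status is not a complete answer.

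Stronger assumptions also give larger numbers. With Black shares of 10% in wild-type and 70% in carriers and a 25-point ancestry effect, the bias is 25 × 0.60 = 15 points and false positives reach 32%. A wild-type v homozygote contrast would carry more bias than the pooled one: at 10/30/50% it is 10 to 20 points × 0.40 = 4 to 8 points.

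What stands is that no race adjustment is planned, unequal ancestry is likely, and a table of race by genotype would be sensible reporting. The documents do not describe the report's tables, so its absence from the plan does not mean it will be missing. What does not stand is the step from imbalance to bias. The range from 0 to 15 points is set entirely by assumed shares and an assumed ancestry effect. In the most extreme case the remedy is also at its weakest, with adjusted power down to 69%.

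**Conclusion.** The concern does not hold as a fault in the plan. Ancestry imbalance between genotype groups is likely, but confounding also needs an ancestry effect on the AUC ratio outside \*6, and neither document gives one. On what is documented the bias may be zero; every non-zero figure above rests on assumed shares and effects. The suggested remedy would leave the unadjusted ANOVA as primary, so the primary result would not change. With 30 subjects, neither a stable nor a shifted adjusted estimate would settle the matter. Naming a race covariate is a preference on which reasonable statisticians differ. The conclusion would change if there were evidence of a sizeable ancestry effect on ketamine metabolism independent of CYP2B6\*6; these documents contain none.

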4.7 Inclusion of Children

Children <18 yr will not be studied in this pilot investigation because there is no direct benefit to them, and the study aims address only adults.

STATISTICAL ANALYSIS PLAN: CYP2B6 Polymorphisms in Ketamine

7/9/13

Primary outcome measures will be ketamine metabolism, measured as plasma norketamine/ketamine concentration-time $AUC_{0-\infty}$ ratio, by *CYP2B6*6* hetero or homozygote genotype. Secondary outcome measures will include ketamine enantiomers area under the plasma concentration curve ($AUC_{0-\infty}$), maximum plasma concentration, apparent oral clearance (and by *CYP2B6*6* hetero or homozygote genotype) and norketamine enantiomers formation clearances (and by genotype). Area under the curve (AUC) of plasma ketamine concentration is determined by noncompartmental methods using nonlinear regression analysis. Clearance is dose/AUC.

Plasma and urine ketamine and metabolite concentrations are analyzed by noncompartmental methods. Outcome measures in wild-type and *CYP2B6*6* carriers will be evaluated by ANOVA. If the hypothesis is correct, we will observe diminished ketamine metabolism and clearance in *CYP2B6*6* carriers.

Sample size calculation is based on the comparison of two groups, genetic variants versus controls. Derived from the belief that detection of a 30% difference in metabolism would be clinically significant and calculating a standard deviation of 25% it is estimated that 12 patients per group is an adequate sample size.

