1. SYNOPSIS

Study Title	Role of CYP2B6 polymorphisms in ketamine metabolism and clearance
Objective	To determine the effects of cytochrome P4502B6 (CYP2B6) genetic variants on ketamine metabolism and clearance
Study Design	Single-center, open label, single-session study to evaluate ketamine pharmacokinetics in subjects with known CYP2B6 genotype
Study Period	Planned enrollment duration: Approximately 3 months. Planned study duration: 1 day per subject
Number of Patients	Approximately 40 healthy volunteers identified by CYP2B6 genotyping by HRPO-approved screening
Inclusion and Exclusion Criteria	
Inclusion Criteria
 
 a) 18-50 yr old b) CYP2B6*1/*1, CYP2B6*1/*6 or CYP2B6*6/*6 genotype c) Good general health with no remarkable medical conditions d) BMI < 33 e) Provide informed consent 
Exclusion Criteria
 
 a) Known history of liver or kidney disease b) Use of prescription or non-prescription medications, herbals, foods or chemicals known to be metabolized by or affecting CYP2B6 c) Females who are pregnant or nursing d) Known history of drug or alcohol addiction (prior or present addiction or treatment for addiction) e) Direct physical access to and routine handling of addicting drugs in the regular course of duty (a routine exclusion from studies of drugs with addiction potential)
Study Medication Administration	Subjects will be studied on one occasion at Washington University in St. Louis School of Medicine for administration of study drugs and blood collection. Study drug is oral ketamine HCl solution (0.4 mg/kg)
Measurements	Plasma samples are obtained for 12 hr after ketamine for measurement of parent drug and metabolite concentrations. A 24hr urine collection is also obtained. Subjective self-assessment of ketamine effect is performed using visual or verbal analog scales. Ketamine and metabolite concentrations are determined by stereoselective LC-MS/MS.
Outcomes	Primary: Plasma norketamine/ketamine AUC ratio Secondary: Plasma ketamine enantiomers and metabolite AUC, maximum concentration, apparent oral clearance, and metabolite formation clearances. Influence of CYP2B6*6 hetero or homozygote genotype on above primary and secondary outcomes

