2.5.3 Primary Outcome Measure

Ketamine metabolism, measured as plasma norketamine/ketamine concentration-time AUC_{0-∞} ratio, by *CYP2B6*6* hetero or homozygote genotype.

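### The SAP calls 12 per group adequate for a two-group comparison, but the protocol plans three genotype groups of 10, and the adequacy claim does not reach the genotype-specific comparisons

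*SAP*

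**What the plan says.** **SAP, sample size paragraph.** The basis is given as "Sample size calculation is based on the comparison of two groups, genetic variants versus controls". The inputs follow: "Derived from the belief that detection of a 30% difference in metabolism would be clinically significant and calculating a standard deviation of 25" per cent. The conclusion is that "it is estimated that 12 patients per group is an adequate sample size". The paragraph gives no total, alpha, sidedness, power or analysis scale.

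**Protocol 2.5.6.** "This is a pilot study. We plan to study 30 evaluable subjects", split as 10 wild-type, 10 heterozygotes and 10 homozygotes. Sections 2.3 and 2.4.1 repeat thirty evaluable.

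**Protocol synopsis.** "Approximately 40 healthy volunteers identified by CYP2B6 genotyping by HRPO-approved screening", without saying whether these are enrolled or evaluable.

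**Which comparison.** The hypothesis in Protocol 2.1 treats "hetero or homozygotes" as one variant class. Protocol 2.5.5 and the SAP say that outcomes in wild-type and "carriers will be evaluated by ANOVA". The primary outcome in Protocol 2.5.3 and the SAP is to be reported by "hetero or homozygote genotype". Neither document names a contrast or says how multiple comparisons would be handled.

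**The concern.** Twelve per group makes 24 subjects in two groups or 36 in three. Neither is 30 or about 40, and nothing links the figures. Whatever is done with the variant groups, the protocol's wild-type group is 10, so the SAP describes as adequate a size that the design does not deliver for controls.

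The text also leaves three tests of the primary outcome open: pooled carriers against wild-type, a three-group F test, and each genotype against wild-type. The SAP sized only a two-group comparison. A reader who carries its adequacy statement over to the genotype-specific results would credit them with a justification that was never made. If the contrast is still unnamed when the data arrive, it could be chosen after seeing them.

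**Working it through.** **Inputs.** From the SAP: difference 30 and SD 25, both taken as percentages of the wild-type mean with a common SD, so d = 30/25 = 1.2; 12 per group. From Protocol 2.5.6: 10/10/10. Assumed, because not stated: two-sided 5%, untransformed scale, equal variances.

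**1. Reproduce 12.** With the noncentral t distribution, noncentrality = d / √(1/n₁ + 1/n₂) = 1.2/0.408 = 2.94 on 22 df. Power is 80.2%; 11 per group gives 76.3%. So 12 is the smallest group size reaching 80%, and the arithmetic is sound for one 1:1 comparison. These assumptions are not the only ones that yield 12:
- one-sided 5%, 90% power, normal approximation: 2(1.645 + 1.282)²/1.2² = 11.9;
- log scale, CV 25%, ratio 0.70, two-sided 5%, 90% power;
- log scale, CV 25%, ratio 1.30, one-sided 5%, 80% power.

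The assumptions actually used therefore cannot be recovered from the figure.

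**2. Precision, whatever the alpha, sidedness or scale.** The standard error is proportional to √(1/n₁ + 1/n₂).

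| Contrast | Factor | Against 12 v 12 |
|---|---|---|
| 12 v 12 (SAP) | 0.408 | – |
| 10 v 20 (pooled carriers) | 0.387 | 5.1% smaller |
| 10 v 10 (one genotype) | 0.447 | 9.5% larger |

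**3. Power.** On the log scale σ = √ln(1 + 0.25²) = 0.246.

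| Contrast | Two-sided 5%, untransformed | One-sided 5%, untransformed | Log, ratio 0.70, two-sided 5% | Log, ratio 1.30, two-sided 5% |
|---|---|---|---|---|
| 12 v 12 | 80.2% | 88.5% | 92.4% | 70.4% |
| 10 v 20 | 84.9% | 91.6% | 95.0% | 75.7% |
| 10 v 10 | 71.8% | 82.5% | 86.5% | 61.6% |

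For 10 v 10 in the first column, using the three-group error term (27 df) gives 73.5%. Bonferroni for two comparisons (2.5% each) gives 60.0%, or 62.4% with 27 df. The ratio 1.30 column is shown for range only; the hypothesis is of reduced metabolism.

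**4. Three-group F test at 10/10/10.** With means 100/70/70, the grand mean is 80 and the noncentrality is 10 × (20² + 10² + 10²)/25² = 9.6 on 2 and 27 df. Power is 74.9%. On the log scale at ratio 0.70 it is 89.6%.

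**5. If 12 per genotype was meant.** The total is 36. Each genotype against wild-type has 80.2% and the F test (100/70/70) 83.5%, both two-sided 5%, untransformed.

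**6. Interval width.** For one genotype against wild-type at 10 v 10, SD 25, 27 df, the 95% CI half-width is 2.052 × 25 × √(1/10 + 1/10) = 22.9 percentage points.

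**The case against.** The strongest reply is that the comparison the SAP sized is met. The hypothesis, the analysis sentence and the sizing sentence all point to variants as one class against wild-type, and for that contrast 10 v 20 is more precise than 12 v 12. This stands. A reader might infer from 10 being less than 12 that the study is underpowered, or that 12 was miscalculated. The documents support neither.

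A shortfall for the other tests also depends on assumptions. The SAP sets no power target, and 10 v 10 exceeds 80% on a one-sided test or on the log scale at ratio 0.70. This stands too: the SAP does not address these tests, which is different from showing that they are inadequate.

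A reader might set 40 against 30 as a plain contradiction. It need not be one. Dropouts are replaced (Protocol 2.4.3 and 3.2) and rare genotypes may be added (2.2 and 2.3.1), so enrolment can exceed the evaluable number. No section says that this is what 40 counts, however, and it would not explain 12.

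A smaller heterozygote effect might seem to undermine the pooled contrast: with falls of 15% and 30% (mean 22.5%) its power is 61.1% (27 df). But 12 v 12 has only 55.9% at the same mean fall. The loss comes from the smaller effect, which is assumed here and appears in neither document, and not from the protocol's group sizes.

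Finally, the protocol calls this a pilot. That limits the importance of the point, but the SAP still makes a formal adequacy statement, and it should match the planned groups.

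**Conclusion.** Minor, but wrong as written. The SAP's 12 per group does not match the protocol's 10 wild-type subjects, and the assumptions behind 12 are not stated. For pooled carriers the mismatch does no harm: the standard error is 5.1% smaller than the one the SAP sized. For each genotype against wild-type it is 9.5% larger. Both statements need only equal variances. The power figures of 84.9% (pooled), 71.8% (single genotype; 60.0% with Bonferroni) and 74.9% (F test, both variant groups 30% lower) rest further on a two-sided 5% test, the untransformed scale and the SAP's 30% and 25%. The supportable conclusion is that the adequacy claim covers one two-group comparison and does not extend to the genotype-specific comparisons named in the primary outcome.

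**What to change.** 1. Reconcile the SAP's 12 per group with the 10/10/10 of Protocol 2.5.6, and say in the synopsis what approximately 40 counts.
2. If 30 evaluable is confirmed, replace the SAP's size sentence with one for 10/10/10 that states alpha, sidedness, scale and the resulting power. At two-sided 5%, untransformed, that is about 85% for pooled 10 v 20 (mean carrier difference 30%) and about 72% for each genotype against wild-type, unadjusted.
3. Name the primary ANOVA contrast in Protocol 2.5.5 and the SAP. Pooled carriers against wild-type is the option the SAP's sizing supports. Because the primary outcome is worded by genotype, the choice is the sponsor's.
4. Report each genotype against wild-type with a 95% CI, and note the expected half-width of about 23 points.
5. Align the synopsis and Protocol 2.5.3 with the choice.

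**Cost.** If 30 is confirmed, this is wording only, and the downside is a less favourable stated power for single-genotype comparisons. If 12 per genotype was intended, 36 − 30 = 6 more evaluable subjects are needed, and Protocol 2.3, 2.4.1 and 2.5.6 must change as well.
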